2.1.1 Phase I run in

Both drugs are FDA approved for other disease indications, with safety and tolerability well described at the approved doses. Therefore the limited phase I portion of this study aims to assess the safety and tolerability of this drug combination at their established doses along with concurrent radiation. There will be no dose escalation cohorts within this phase I run in group.

The first six patients will constitute the phase I portion of this study. These initial 6 patients will be assessed for dose limiting toxicities (DLTs, defined in Section 2.1.1.1)

from the start of study treatment until the start of cycle #2 concurrent cisplatin/radiation and pembrolizumab. After these first 6 patients initiate cycle #1, enrollment to the study will be temporarily halted, and a formal DLT evaluation of all 6 patients will be conducted.

If ≤ 2 of these six patients experience DLTs after completion of cycle #1 concurrent cisplatin/radiation and Pembrolizumab, then the study will proceed to the phase II portion, using Pembrolizumab 200mg IV Q21 days and cisplatin 100mg IV each 21 day cycle.

If > 2 of these first 6 patients experience a DLT upon completion of cycle #1, the protocol will be amended to investigate use of pembrolizumab 200 mg IV Q 21 days subsequent to completion of chemoradiation. (3-6 weeks after last dose of radiation) (upon Merck approval)

Only upon completion of the DLT evaluation for these first 6 patients and the determination of appropriate Phase II dose, will enrollment reopen for the phase II expansion.

If toxicity results are unclear, we will allow 6 additional patients into Phase I portion (6 + 6). The second cohort will be assessed based on above definitions for DLTs. Unclear toxicity can include (but not limited to) adverse effects that are considered secondary to cisplatin or radiation and per protocol are not considered DLT (see section 2.1.1.1 for definition of DLT) , however, the investigator strongly feels they could be related to study drug or exacerbated by concurrent use of study drug and chemoradiation. This investigator initiated study will be under the oversight of the University of Cincinnati IRB and Data and Safety Monitoring committee.

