2.1.2 Phase II expansion

After the first 6 patients have been assessed for DLTs upon completion of cycle 1 of treatment, and the appropriate Cisplatin dose and Pembrolizumab dosing determined

for phase II expansion, an additional 41 patients with locally advanced larynx squamous cell carcinoma will be enrolled in this phase I/II study. The entire cohort will be used to assess the safety and efficacy outcomes of interest. Safety stopping rules will be applied in the event of excessive toxicity leading to inability of patients to receive at least 2 doses of cisplatin and complete radiation therapy. If radiation treatment breaks are required, greater than a 10 day radiation treatment break in 6 or more patients will also initiate early stop for safety evaluation.

Patients will be evaluated 14 weeks after completion of radiation (14 ± 2 week after completion of radiation) with radiographic imaging to assess response to treatment. All imaging will be assessed using Response Evaluation Criteria in Solid Tumors (RECIST) 1.1 Adverse events will be monitored throughout the trial and graded in severity according to the guidelines outlined in the NCI Common Terminology Criteria for Adverse Events (CTCAE) version 4.0.

After the end of treatment, each patient will be followed for a minimum of 30 days for adverse event monitoring (serious adverse events will be collected for up to 90 days after the end of treatment). Subjects will have post-treatment follow-up for laryngectomy event and survival status for two years.

Participation in this trial will be dependent upon supplying tumor tissue from a formalin-fixed specimen. Newly obtained formalin-fixed specimens are strongly encouraged 14-20 days after first dose of Pembrolizumab prior to initiation of cisplatin and radiation unless clinically deemed unsafe by the treating physician. The specimen will be evaluated for expression status of PD-L1.

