statistically significant. Overall survival rates were similar at 75% at 2 years for all treatment groups [11]. In a recent update to the RTOG 91-11 study, composite end point of LFS for the concurrent chemotherapy group was 74% and 63% at 1 and 2 years respectively. At 10-year follow up, there is no significant difference between the concomitant cisplatin/ RT arm (23.5%) and the induction arm (28.9%). LFS was significantly worse for RT group (17.2%) versus both the induction group and the concomitant group, confirming role of systemic therapy in treatment of laryngeal cancer. [12]

More recent studies that have introduced more aggressive induction chemotherapy regimens [TPF (taxane, cisplatin, and 5-fluorouracil)] to improve on laryngeal preservation rates compared to induction chemotherapy arm of RTOG 91-11 (3-year LFS 70% vs 57%), however, these regimens carry higher adverse events without improvement in PFS or OS. [13]

In the event of locally recurrent, residual disease, or dysfunctional larynx after completion of chemo radiation, salvage laryngectomy is considered standard treatment. However, there appears to be a significantly worse survival outcome for those patients undergoing laryngectomy after patients having been exposed to chemotherapy in combination with radiation [12].

Thus, treatment paradigms for larynx cancer have continued to change since 1991 resulting in variability in the treatment sequence and type of therapeutic modalities used. [14]. Unlike most other malignancies, a recent review of the latest National Cancer Data Base (NCDB) has demonstrated worsening survival outcome of larynx cancer patients in recent years with a 5-year survival at 59% compared to 67% in 1985. These findings may, to some extent, reflect changes in practice patterns over the last two decades [1]. In addition, some other retrospective studies suggest a possible inferior oncologic outcome in patients who choose organ preservation compared to a more traditional upfront surgery (TL) with 2-year disease specific survival and overall survival (70% vs 64%) and (64% vs 57%) respectively. [15]

These findings suggest a need for further investigation and development of more successful curative organ preservation approaches. Despite multiple trials over the last two decades, overall rates of cure and organ preservation remain suboptimal without much improvement since introduction of concurrent chemo radiation in the landmark RTOG 91-11 study.

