7.1.5.4.1 Survival Follow-up

Once a subject experiences confirmed disease progression or starts a new anti-cancer therapy, the subject moves into the survival follow-up phase and should be contacted by telephone every 12 weeks (12± 1 week) to assess for survival status until death, withdrawal of consent, or the end of the study, whichever occurs first.

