8.0 STATISTICAL ANALYSIS PLAN

8.1 Statistical Analysis Plan Summary

The primary endpoint is laryngectomy-free survival (LFS) at 18 month. LFS for standard of care is approximately 70%; the trial hypothesis is that LFS at 18 month can be improved to at least 85% using the experimental agent. Forty seven patients are required to identify this improvement in 18 month LFS using a one-sided test with 10% significance and 80% power. This calculation is based on a non-parametric LFS distribution, and assumes that it will take 18 months to accrue all 47 patients, and that an additional 6 months of follow-up will be done after the last patient is enrolled.

Study size was calculated using the SWOG calculator for “one-arm nonparametric survival”: <http://www.swogstat.org/statoolsout.html>

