8.2 Statistical Analysis Plan

Safety run-in phase: Although PD-1 inhibition is not expected to increase the toxicity of chemoradiation therapy, clinical trials of pembrolizumab combined with cisplatin and radiation for locally advanced head and neck carcinoma have not been conducted. In order to protect against unexpected problems a run-in safety analysis will be performed prior to completing the rest of the first stage of study. This safety analysis will occur after 6 analyzable patients are entered into study. Pembrolizumab will be administered initially at the recommended phase II dose of 200 mg q 3 weeks. If more than 2 dose-limiting toxicities (DLTs) in the cohort of 6 patients then pembrolizumab will be given subsequent to completion of chemoradiation. In the event of 0-2 DLT events, the study will proceed as planned. A DLT will be defined as a \geq grade 3 (CTCAE, v.4) adverse event that is definitely, probably, or possibly related to study drug, excluding grade 3 tumor flare and toxicities that are strongly associated with concurrent radiation and cisplatin (for example rash, mucositis, radiation dermatitis).

LFS will be estimated using the Kaplan-Meier method. The point estimate and standard error will be obtained from the Kaplan-Meier curve and a 95% confidence interval will be calculated to estimate 18-month LFS. A z-test will be used to test the primary hypothesis of improvement in 18- month LFS from 70% to 85%.

One-year LFS, Progression-free survival, overall survival, event-free survival, and patterns of failure will be estimated using the Kaplan-Meier method. Complete response at 3 months will be estimated with an exact 95% confidence interval. For correlative studies, prognostic factors for complete response will be identified using logistic regression analysis. Prognostic factors for outcomes will be identified using Cox proportional hazards analysis.

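### The primary z-test for 18-month LFS names no scale, variance form or analysis date; read naturally, its type I error is about 14% at the 24-month sizing cut, not the stated 10%

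*Combined protocol and SAP*

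**What the plan says.** Section 8.1 takes 18-month LFS as about 70% under standard care and at least 85% under the experimental regimen. It requires 47 patients "using a one-sided test with 10% significance and 80% power". The calculation assumes 18 months of accrual and that "an additional 6 months of follow-up will be done after the last patient is enrolled", which places the sizing cut at month 24.

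Section 8.2 describes the analysis: "The point estimate and standard error will be obtained from the Kaplan-Meier curve", followed by "A z-test will be used to test the primary hypothesis of improvement in" 18-month LFS. It does not say whether the test is on the survival scale or a transformed one, whether the standard error is estimated from the data or fixed at its null value, or when the analysis takes place.

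The durations elsewhere do not settle the date. Section 1.0 gives a 24-month trial and also 24 months of participation per patient. Section 2.1.2 says: "Subjects will have post-treatment follow-up for laryngectomy event and survival status for two years". A month-24 cut cannot supply that for patients enrolled late.

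**The concern.** The stated 10% and 80% belong to a particular test at a particular time, and section 8.2 defines neither. With 47 patients and heavy censoring before month 18, these choices change the operating characteristics by several points. They can also reverse a borderline result. The trial is open-label with one arm, so an unspecified choice could be made after the data have been seen.

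If the most literal version of the test is used, a regimen no better than 70% would be declared promising about one time in seven rather than one in ten.

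**Working it through.** **Inputs.** From 8.1: n = 47, null 0.70, alternative 0.85, one-sided 10%, 80% power, accrual 18 months, cut at month 24. Assumed: uniform entry, no dropout in the main case, and Weibull LFS with several shapes (1.0 is exponential). The only LFS curve in the protocol is in 4.1.1: "composite end point of LFS for the concurrent chemotherapy group was 74% and 63% at 1 and 2 years respectively". It implies shape = log2(ln 0.63 / ln 0.74) = 0.62.

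**Reproducing 47.** Let V(S) = ∫₀¹⁸ h(t) / [S(t)G(t)] dt. Here h is the hazard and G the chance of not yet being censored: 1 up to 6 months, then (24 − t)/18. For exponential LFS, V = 0.635 under the null and 0.257 under the alternative.

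On the log-log scale:
- s0 = √0.635 / |ln 0.70| = 2.234
- s1 = √0.257 / |ln 0.85| = 3.117
- d = ln(0.3567 / 0.1625) = 0.786
- n = [(1.2816 × 2.234 + 0.8416 × 3.117) / 0.786]² = 48.7
- Power at 47 = Φ[(0.786 × √47 − 1.2816 × 2.234) / 3.117] = 79.1%

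Over shapes 0.7 to 1.5, n runs from 44.9 to 53.9. So 47 is consistent with a log-log large-sample calculation. The same formula on the untransformed scale gives 51.6.

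**The tests as they would be run.** Both use the estimated Greenwood SE and reject if z > 1.2816.
- Plain: z = (Ŝ − 0.70) / SE
- Log-log: z = [ln(−ln 0.70) − ln(−ln Ŝ)] / [SE / (Ŝ |ln Ŝ|)]

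At month 24 only about 47 × 0.70 × 1/3 = 11 patients are still at risk at 18 months under the null. Simulated type I error / power, 100,000 trials per cell (Monte Carlo SE about 0.1 point):

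| Cut | Shape | Plain | Log-log |
|---|---|---|---|
| Month 24 | 0.62 | 14% / 84% | 10% / 78% |
| Month 24 | 0.7 | 14.1% / 83.7% | 10.3% / 77.6% |
| Month 24 | 1.0 | 14.1% / 81.7% | 10.3% / 74.7% |
| Month 24 | 1.5 | 14.4% / 79.2% | 10.3% / 71.4% |
| Month 30 | 0.7 | 12.7% / 90.1% | 8.3% / 85.5% |
| Month 30 | 1.0 | 12.7% / 89.5% | 8.7% / 85.2% |
| Month 30 | 1.5 | 12.6% / 88.6% | 9.2% / 84.3% |
| Month 36 | 0.7-1.5 | 12.3-12.5% / 92% | 6.6-6.7% / 84% |

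**Sensitivity.** With 5% yearly dropout (exponential), month 24 gives plain 14.5% / 81% and log-log 10.5% / 73%. Section 2.1.1 also says that, after the first six patients, "enrollment to the study will be temporarily halted, and a formal DLT evaluation of all 6 patients will be conducted"; it gives no length. An assumed two-month pause inside the 18 months gives plain 15.1-15.6% and log-log power 68-75%. A three-month halt, with six patients in the first three months and 41 in the last twelve, gives plain 17.4% and log-log power 69.9% (exponential). If the pause instead stretches accrual to 20 months and the cut moves with it, the figures barely change (plain 14.2% / 82%, log-log 10.3% / 75%).

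**Complete 18-month data.** With 37/47 = 0.787 event-free, SE = √(0.787 × 0.213 / 47) = 0.0597.
- Plain z = 0.0872 / 0.0597 = 1.46, which rejects.
- Log-log z = 1.26, which does not.
- Exact binomial p = 0.124, which does not.

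The plain test therefore rejects at 37 or more (12.4% / 91.5%), the log-log test at 38 or more (6.7% / 84.2%). For n = 45 to 49 the plain type I error is 9.3, 14.3, 12.4, 10.7 and 9.2%, so the 12.4% partly reflects discreteness.

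**The case against.** Four objections carry weight.

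1. A reader might infer that the log-log version has 75% power. That figure assumes a constant hazard. At the falling hazard implied by 4.1.1, simulated power is about 78%, and the large-sample formula gives 81.7% at n = 47. Two time points fix the shape only roughly, so the range 71-78% is the fair statement.

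2. A reader might infer that no z-test meets both targets at month 24. That goes too far. With the standard error fixed at its null value, the plain test gives 9.7% / 77.5% for exponential LFS and 9.8% / 80.0% at shape 0.7. Section 8.2 points the other way, since it takes the standard error from the Kaplan-Meier curve, but this shows that the variance form must be written down too.

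3. The null is itself approximate. Interpolating the 4.1.1 figures at constant hazard gives √(0.74 × 0.63) = 0.683 at 18 months. If true LFS is 0.68 to 0.685, the plain test at month 24 rejects 9.5 to 10.8% of the time. For an uncontrolled screen, 14% against 10% will seldom change the decision. This limits the weight of the point but does not remove it, because 8.1 states its error rate against 70%.

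4. The 37/47 example is a single boundary outcome. That is fair: it shows that the choice can matter, not how often. At month 24 the two scales disagree in about 4% of null trials and 6-8% of alternative trials.

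**Conclusion.** The point holds. Section 8.2 leaves the primary test under-specified, and its most natural reading does not deliver the 10% type I error stated in 8.1. The error is about 14% at the month-24 sizing cut and 12-13% later, so waiting alone does not cure it. A log-log test with estimated SE controls the error at month 24, at about 71-78% power. These figures assume n = 47, uniform entry, no dropout and Weibull shapes of about 0.6 to 1.5.

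Two stronger readings are not supported. The sample size is not wrong: 47 is within two patients of the log-log large-sample figure for exponential LFS. And the documents do not say that the primary analysis will be at month 24; that is how the trial was sized, and the two-year follow-up in 2.1.2 would allow a later date.

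The plan should be changed, with moderate weight given the single-arm phase II setting. Whether telephone contacts after progression (7.1.5.4.1) capture laryngectomy is a separate data-collection matter and adds nothing to this point.

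**What to change.** 1. In 8.2, prespecify a one-sided 10% test of 18-month LFS against 0.70 on the complementary log-log scale, with the Greenwood standard error estimated from the data.

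2. Fix one primary analysis date, for example 12 months after last enrolment (month 30 under planned accrual). Align the durations in 1.0 and 8.1 with the two-year follow-up in 2.1.2. Type I error is then about 8-9% and power about 84-85%. With the assumed two-month pause, 5% yearly dropout, or both, it remains 8.4-9.2% and 83.5-85.2%.

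3. If month 24 is kept, restate the operating characteristics with their accrual, dropout and hazard assumptions: about 14% type I error for the plain test, or about 10% type I error and 71-78% power for the log-log test.

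The cost of the first two changes is SAP wording and a readout six months later than the sizing assumption. No patients are added. The third change costs a sentence.

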3.2 Secondary Objective(s)

- (1) **Objective:** Estimate the one-year laryngectomy-free survival in locally advanced laryngeal squamous cell carcinoma (LA-larynx SCC).
- (2) **Objective:** Estimate overall survival and progression free survival in patients enrolled in the study
- (2) **Objective:** Estimate 3-month complete response rate (CR) in patients enrolled in the study
- (3) **Objective:** Estimate event –free survival (events include death, persistent or progressive disease, laryngectomy)

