3.3 Exploratory Objective

1. **Objective:** Explore peripheral T cell phenotype at baseline and after treatment with Cisplatin, radiation, and Pembrolizumab.
Hypothesis: T cell phenotype is altered after exposure to Cisplatin, radiation, and Pembrolizumab, and will correlate with treatment response.
2. **Objective:** Measure expression of the proteins in the PD-1 family on baseline tumor samples and on treatment biopsies.
Hypothesis: There is a relationship between response to Pembrolizumab and PD-1 protein family expression in both pre- and post-treatment tumor samples. Cisplatin-radiation concurrent with Pembrolizumab impacts the expression of PD-1 family of proteins.
3. **Objective:** Measure circulating tumor DNA in pre-treatment, during treatment, and post-treatment blood samples.
Hypothesis: There is a relationship between response to Pembrolizumab and circulating tumor DNA level in both pre- and post-treatment tumor samples.
4. **Objective:** Explore Tumor infiltrating immune cell phenotypes and global gene expression (including 12-gene signature) by RNAseq on baseline tumor samples and on treatment biopsies.
Hypothesis: Tumor infiltrating immune cell phenotypes and global gene expression is altered after exposure to Pembrolizumab, and will correlate with treatment response.
5. **Objective:** Explore patterns of disease recurrence after treatment with Cisplatin, radiation, and Pembrolizumab.
Hypothesis: Patterns of recurrence of disease is altered after exposure to Pembrolizumab when added to standard Cisplatin and radiation therapy.
6. **Objective:** Explore rates of speech and swallowing dysfunction after completion of treatment with Cisplatin, Radiation, and Pembrolizumab.
Hypothesis: Rates of speech and swallowing dysfunction is improved after completion of treatment with Cisplatin, Radiation, and Pembrolizumab.
7. **Objective:** Explore PET scan findings after completion of treatment with Cisplatin, Radiation, and Pembrolizumab

Hypothesis: There is a relationship between post treatment PET scan and clinical benefit in patients treated with Cisplatin, Radiation, and Pembrolizumab.

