Laryngeal squamous cell carcinoma is unique in the setting for which surgical options are less appealing due to long-term morbidities associated with a total laryngectomy (tracheostomy and loss of voice). Chemo-radiation alone may not be sufficient to avoid surgery and allow for a long-term survival of patients with a functional larynx. This disease is also unique in the setting that it is highly associated with smoking and genetic complexity, making it a favorable target for immune modulators. In addition, biologic correlative testing is feasible due to the accessibility of tumor tissue by biopsy and any specimens from patients undergoing laryngectomy for residual/ progressive or dysfunctioning larynx.

We propose a single arm phase II study to test the hypothesis that the addition of Pembrolizumab to chemoradiation enhances the local effects of standard therapy in laryngeal HNSCC, ultimately allowing for higher rates of functional organ preservation in this population, and leading to improved quality of life. In addition, we hypothesize that adding Pembrolizumab to chemo radiation may result in immune-mediated regression

of micrometastatic disease and lower rates of systemic relapse, similar to what has previously been described in distant untreated melanoma lesions [21] Therefore, we will examine not only laryngectomy-free survival and event-free survival endpoints [including death, persistent disease or progression, laryngectomy (partial or total), and feeding tube dependence], but also pattern of in and out of field tumor growth in these patients. Finally, we will examine exploratory correlative studies that will provide valuable insight into the effects of chemo radiation in combination with PD1 inhibitor on laryngeal carcinoma microenvironment, and the association of tumor response and overall clinical benefit with adaptive PD-L1 tumor expression, immune infiltration, cytokine expression profiles, and genomic signature of tumors. We hypothesize that chemo radiation affects expression of PD1/PD-L1 on tumor infiltrating immune cells detected by IHC and subsequently increases PD-L1 expression on the tumor cells, which will predict response to chemo radiation and PD-1 inhibitor.

We hypothesize by inhibiting PD1 ligands, PDL1 and PDL2, we will activate immune system and allow for better anti-tumor effect, finally resulting in improved laryngectomy-free survival with fewer side effects.

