7.1.5.4 Follow-up Visits

Subjects who discontinue trial treatment for a reason other than disease progression will move into the Follow-Up Phase and should be assessed every 12 weeks (12± 1 week) by exam to monitor disease status. Imaging should be performed at 14 weeks (+/-2 weeks) since last treatment (radiation or drug therapy). Further imaging is per decision of treating clinician. Every effort should be made to collect information regarding disease status until the start of new anti-neoplastic therapy, disease progression, death, end of the study.

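### Section 8.2 assigns Kaplan-Meier to patterns of failure without defining failure types or competing events; cumulative incidence by first-failure type would suit exploratory objective 5 better

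*Combined protocol and SAP*

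**What the plan says.** In section 8.2 one Kaplan-Meier sentence covers one-year LFS, progression-free survival (PFS), overall survival (OS), event-free survival (EFS) and patterns of failure: "event-free survival, and patterns of failure will be estimated using the Kaplan-Meier method". The last item matches exploratory objective 5 in section 3.3, "Explore patterns of disease recurrence after treatment with Cisplatin, radiation, and Pembrolizumab", whose hypothesis is "Patterns of recurrence of disease is altered after exposure to Pembrolizumab when added to standard Cisplatin and radiation therapy". No other analysis is given for that objective.

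Three places hint at what the failure types might be:

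- Section 4.1.1 describes recurrence patterns in a historical randomised trial as local versus distant percentages.
- Section 4.2.1 promises to examine "but also pattern of in and out of field tumor growth in these patients".
- Section 4.2.3.2 mentions regional and systemic recurrence as a source of biopsies.

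None of these defines the types for the analysis. No section gives a censoring rule, names competing events or mentions cumulative incidence.

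On data collection, section 7.1.5.4 says: "Every effort should be made to collect information regarding disease status until the start of new anti-neoplastic therapy, disease progression, death". Section 7.1.5.4.1 adds: "Once a subject experiences confirmed disease progression or starts a new anti-cancer therapy, the subject moves into the survival follow-up phase", which consists of telephone contact for survival status. Section 2.1.2 states: "Subjects will have post-treatment follow-up for laryngectomy event and survival status for two years".

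**The concern.** LFS, PFS, OS and EFS are composites: each event of interest ends follow-up as an event, and Kaplan-Meier estimates the probability of remaining free of all of them. A pattern of failure is a different quantity, because it splits failures by type. A patient who dies without recurrence, or who fails first at another site, is no longer at risk of that type as a first failure.

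Kaplan-Meier can be applied here in three ways, and the SAP does not choose between them:

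- Censor deaths and other first failures. One minus Kaplan-Meier then tends to overstate the probability of the type.
- Count every failure and death as an event. The curve is valid, but it is the same for every type and shows no pattern.
- Count death together with one type. The curve then describes a composite, not that type.

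At stake is whether the figures reported for objective 5 can be read as the share of patients who fail first in each way.

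**Working it through.** **Inputs from the documents.** Section 8.1 gives 18-month LFS of 70% (standard of care) and 85% (hypothesis), with 47 patients. Section 4.1.1 gives 63% two-year LFS for the concurrent arm of a historical randomised trial. It also gives, for the induction-chemotherapy group of another trial, local recurrence of 12% and distant metastasis of 11%. That split comes from a different regimen, and no planning split is given for this trial.

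**The plan's own figure.** There is none for patterns of failure. The sample size was checked for completeness with a one-sided 10% test, 80% power, exponential LFS, 18 months of accrual and 6 of follow-up. On the log(-log) scale this gives 48.7 patients, and a power of 0.791 at 47. That is close to the stated 47 and 80%, and nothing below depends on it.

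**Assumptions.** LFS stands in for freedom from any failure or death. Cause-specific hazards are proportional. Each type takes a share *t* of the total hazard, with *t* set at a quarter, a third or a half. Deaths and other first failures are censored.

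**Formulas.** With event-free probability S and H = −ln S:

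- cumulative incidence of the type as first failure = t(1 − S)
- one minus Kaplan-Meier for the type = 1 − exp(−tH)

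Example, S = 0.70 and t = 1/3: H = 0.3567. Cumulative incidence = 0.30/3 = 10.0%. One minus Kaplan-Meier = 1 − exp(−0.1189) = 11.2%.

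| S | t | Cumulative incidence | One minus KM | Excess (points) |
|---|---|---|---|---|
| 0.85 (18 mo) | 1/4 | 3.75% | 3.98% | 0.23 |
| 0.85 | 1/3 | 5.00% | 5.27% | 0.27 |
| 0.85 | 1/2 | 7.50% | 7.80% | 0.30 |
| 0.70 (18 mo) | 1/4 | 7.50% | 8.53% | 1.03 |
| 0.70 | 1/3 | 10.00% | 11.21% | 1.21 |
| 0.70 | 1/2 | 15.00% | 16.33% | 1.33 |
| 0.63 (24 mo) | 1/4 | 9.25% | 10.91% | 1.66 |
| 0.63 | 1/2 | 18.50% | 20.63% | 2.13 |

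**Effect of timing.** Proportional hazards is only one case. Take S = 0.70 and a type with a true risk of 15%. If all competing events come first, one minus Kaplan-Meier is 0.15/(1 − 0.15) = 17.6%. If all come last it is 15.0%, with no excess. The range is therefore 0 to 2.6 points.

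**Against sampling error.** At a 10% rate with 47 patients the 95% half-width is 1.96 × √(0.10 × 0.90/47) = 8.6 points, before any widening from censoring. The exact 95% interval for 5 of 47 is 3.5% to 23.1%.

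**Does the follow-up point to a rule?** Sections 7.1.5.4 and 7.1.5.4.1 track disease status up to first progression and then only survival by telephone. A later failure of another type would not be captured systematically. These data fit a first-failure analysis, in which type-specific Kaplan-Meier curves would naturally censor at the first failure of another type. That is an inference about practice, because the SAP does not say it.

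**The case against.** The strongest reply is that section 8.2 never says type-specific curves will censor other events, so the plan shows a gap and not a stated error. That stands. A reader might infer that the reported rates will be overstated. The documents do not support this: it depends on an unwritten rule, and the excess is zero for any type whose failures all come before the competing events. With about 7 to 14 events expected (15% to 30% of 47), that could happen.

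It can also be said that objective 5 names no estimand, and that a curve censoring other failures is a legitimate transform of the cause-specific hazard. This is fair. Such a curve can help in asking whether treatment alters one failure process, but it does not give the absolute probability of failing in a given way.

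A reader might take section 4.2.1 as proof that the types are in-field and out-of-field. It only suggests so; section 4.1.1 uses local and distant, and section 4.2.3.2 regional and systemic.

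LFS is also an imperfect stand-in. It counts laryngectomy for a dysfunctional larynx, and it need not count a distant recurrence without laryngectomy or death. A total over all types, such as 3 × 11.21% = 33.6% against 30.0% with equal thirds, needs a separate curve for death without recurrence, which the SAP does not plan.

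**Conclusion.** The point holds as a minor one. Kaplan-Meier is not the best method for the item to which section 8.2 assigns it, and the information needed to apply it is missing. Under the censoring rule that best fits the follow-up, the overstatement is about 0.2 to 1.3 points at 85% to 70% event-free, and about 2 points at 63%. These sizes rest on the LFS stand-in, the assumed shares and proportional hazards. They are well below the sampling error at 47 patients.

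A reader might infer that the efficacy conclusions are at risk. They are not: only exploratory objective 5 is touched, and the documents attach no test or threshold to it. The primary z-test, sample size, power and secondary estimates do not change, and Kaplan-Meier remains suitable for LFS, PFS, OS and EFS.

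**What to change.** In section 8.2, take patterns of failure out of the Kaplan-Meier sentence. Report instead the Aalen-Johansen cumulative incidence of each first-failure type with a 95% confidence interval, treating other first-failure types and death without failure as competing events. Name the types (for example local, regional and distant, or in-field and out-of-field), give a rule for simultaneous failures, and record the site of first failure. Leave Kaplan-Meier in place for LFS, PFS, OS and EFS.

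The cost is a short SAP paragraph and a little work in standard software. No section says that the site of first failure is recorded, so one case report form item may be needed. If in-field and out-of-field are chosen, recurrences must also be mapped to the radiation volumes in section 5.2.2.4. The sample size, visits and primary analysis stay as they are.
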